Study visits from Week 1 Day 1 to Week 2 Day 1 should be completed on the designated date [with an allowed "visit window" of +/- 1 day for Week 1 Day 1 and Week 2 Day 1]

Study visits from Week 4 to Week 12 should be completed every 4 weeks on the designated date [with an allowed "visit window" of +/- 2 day]

Study visits after Week 12 (from Week 24) to EOT should be completed every 12 weeks on the designated date [with an allowed "visit window" of +/- 7 days].

Safety follow-up should be completed 30 days from the last dose of study treatment [with an allowed "visit window" of +/- 7 days].

Visit at weeks 62, 74, 86, 98, 110 or 122 that is two weeks post dose escalation should be completed once after dose escalation on the designated date [with an allowed "visit window" of +/- 1 day].

A delayed visit will have no impact on the next planned visit. The next visit should be completed as scheduled in order to avoid accumulation of additional weeks.

Visit name	Category	Protocol Section	Screening Phase	Treatment Phase										EOT (week 144) /Early Discontinuation	Safety follow-up ¹³		
				Screening/ Baseline	Week 1 Day 1	Week 2 Day 1	Week 4	Week 8	Week 12	Week 24	Week 36	Week 48	Every 12 weeks up to week 132 (w60, w72, w84, w96, w108, w120, w132)			Week 62/74/86/98/ 110/122 for patient dose escalating	
Days (+/- X days)			Day -28 to -1	1 (+/- 1 day)	8 (+/- 1 day)	29 (+/- 2 days)	57 (+/- 2 days)	85 (+/- 2 days)	169 (+/- 7 days)	253 (+/- 7 days)	337 (+/- 7 days)	(+/- 7 days)	(+/- 1 day)	(+/- 7 days)	(+/- 7 days)		
Prior/concomitant medications	D	8.2	X	Continuous													
Physical Examinations	S	8.4	X	X		X	X	X	X	X	X	X		X			
Extra medullary Involvement	D		X														
ECOG Performance status	D	8.4.1	X	X		X	X	X	X	X	X	X		X			
Height	D	8.4	X														
Weight	D	8.4	X	X				X	X	X	X	X		X			
Vital signs ¹	D	8.4	X	X	X	X	X	X	X	X	X	X		X			
Laboratory assessments		8.4.2															
Hematology	D	8.4.2	X	X	X	X	X	X	X	X	X	X	X	X			
Chemistry ²	D	8.4.2	X	X	X	X	X	X	X	X	X	X	X	X			
Coagulation	D	8.4.2	X	As clinically indicated													

1. Blood Pressure reading to be taken in the supine position for all visits.
2. Hemoglobin A1c to be collected at screening only.

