1. ***pre-treatment period:*** from day of subject’s informed consent to the day before first administration of study treatment
2. ***on-treatment period:*** from date of first administration of study treatment to 30 days after date of last administration of study treatment (including start and stop date).
3. ***post-treatment period:*** starting at day 31 after last administration of study treatment.

If dates are incomplete in a way that clear assignment to pre-, on-, post-treatment period cannot be made, then the respective data will be assigned to the on-treatment period.

Safety summaries (tables, figures) on the corresponding Safety set include only data from the on-treatment period with the exception of baseline data which will also be summarized where appropriate (e.g. change from baseline summaries). In particular, summary tables for adverse events (AEs) will summarize only on-treatment events, with a start date during the on-treatment period. In addition, a separate summary for death will be provided.

However, all safety data (including those from the pre-treatment and post-treatment) will be listed and flagged as appropriate.

Efficacy summaries on the FAS and FAS 2 (apart from OS and PFS) include data from baseline up to either the last assessment on or before the End of Treatment (EoT) visit or before or on treatment failure, whichever is the earliest.

The efficacy assessments collected post-treatment failure or post-EoT visit are not included in any efficacy analyses (except for OS and PFS analyses). However, they will be listed and flagged as appropriate.

Windows for multiple assessments

Data such as molecular response, cytogenetic response collected over time (including unscheduled visits) will be summarized by scheduled time point. As subjects do not always adhere to the visit schedule, visits will be remapped according to visit windows defined in Tables 2-1 to Table 2-3 of this document to enable by-visit analysis. Only those protocol-defined visits will have the visit window defined. Each assessment (including the end of treatment assessment), either scheduled or unscheduled, will have a mapped visit assigned, as long as study day is available, according to the defined visit window up to the date with data included.

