If more than one assessment is assigned to the same time window, the assessment performed closest to the target date will be used for by-visit statistical analyses. If 2 assessments within a visit window are equidistant from the target date, then the average of the 2 assessments will be used. If multiple assessments are on the same date, then the the average will be used. Data from all assessments (scheduled and unscheduled), including multiple assessments, will be listed.

Table 2-1 Time windows for molecular response

Assessment	Target day of assessment	Time Interval
Baseline	≤ 1	\leq Day 1 [#]
Week 12	85	Day 2 to day 127
Week 24	169	Day 128 to day 211
Week 36	253	Day 212 to day 295
Week 48	337	Day 296 to day 379
Week k (k=60, 72, ...)	$K \times 7 + 1$	Day $k \times 7 - 40$ – $k \times 7 + 43$

Day 1 = Date of randomization
EOT assessments are mapped to the time points as needed.

Table 2-2 Time windows for cytogenetic response

Assessment	Target day of assessment	Time Interval
Baseline	1	≤ Day 1 [#]
Week 48	337	Day 253 to day 420
EOT [*]	EOT	EOT

[#] Day 1 = Date of randomization. Should bone marrow assessments have been performed before the main informed consent is signed but within 56 days of Week 1 Day 1, no further bone marrow sampling will be required at screening and local assessment data will be collected.

^{*} Only required for Early Discontinuation due to lack of response / loss of response

For PRO data time windows will be defined for descriptive summary by visit. If more than one assessment is available in the same time window, the assessment closest to the planned date will be considered. If two assessments are obtained with the same time difference compared to the scheduled visit day, the assessment obtained prior to visit will be considered.

Table 2-3 Time windows for PRO: MDASI-CML

Assessment	Target day of assessment	Time Interval
Baseline	1	≤ Day 1 [#]
Week 4	29	Day 2 to day 57
Week 12	85	Day 58 to day 127
Week 24	169	Day 128 to day 253
Week 48	337	Day 254 to day 421
Week 72	505	Day 422 to day 589
Week 96	673	Day 590 to day 757
Week 120	841	Day 758 to day 925
EOT (Week 144)	1009	Day 926 to day 1009

[#] Day 1 = Date of randomization

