The general rule for the target day of assessment and time interval is: For Week k visit, target day of assessment is defined as $k*7+1$. For the time interval, “Lower limit” = “upper limit of prior applicable visit” +1. “Upper limit” = “target day of current visit” + integer part of (“target day of next applicable visit” – “target day of current visit”)/2.

Last contact date

The last contact date will be derived for subjects not known to have died at the respective analysis data cut-off date using the last complete date among the following:

Table 2-4 Last contact date data sources

Source data	Conditions
Date of randomization	No condition
Start/End dates from further antineoplastic therapy	Non-missing medication/procedure term
Start/End dates from drug administration record	Non-missing dose. Doses of 0 are allowed
Study disposition date	The date of the subject's last protocol assessment performed in the study phase
Any specific efficacy (molecular or cytogenetic) assessment date if available	Evaluation is marked as 'done'
Laboratory/PK collection dates	Sample collection marked as 'done'
Vital signs date	At least one non-missing parameter value
Performance status date	Non-missing performance status
Start/End dates of AE	Non-missing verbatim term

The last contact date is defined as the latest complete date from the above list on or before the respective data cut-off date. The cut-off date will not be used for last contact date, unless the subject was seen or contacted on that date. No date post the cut-off date will be used. Completely imputed dates (e.g. the analysis data cut-off date programmatically imputed to replace the missing end date of a dose administration record) will not be used to derive the last contact date.

The last contact date will be used for censoring of subjects in the analysis of overall survival.

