2.10 Patient-reported outcomes

The patient reported outcomes (PRO) objectives are to compare the impact of treatment on PROs including CML-specific symptoms and health related patient quality of life from baseline through end of treatment in all subjects by using FAS except stated otherwise. The M.D. Anderson Symptom Inventory – Chronic Myeloid Leukemia (MDASI-CML) questionnaire is planned to be administered during screening, at weeks 4, 12, 24, 48, 72, 96, 120 and end of treatment.

The MDASI-CML is a 26 item self-administered questionnaire for adult CML patients. Twenty of the items measure the severity of disease-related symptoms and are scored from 0 (Not present) to 10 (As bad as you can imagine) and 6 items that measure symptom interference with daily life scored from 0 (Did not interfere) to 10 (Interfered completely).

The severity score will be calculated when a subject scores at least 11 items out of the 20 severity items using the formula: (sum of scores for the items answered) / (number of items answered). If a subject scores fewer than 11 items, the severity score will be missing.

The interference score will be calculated when a subject scores at least 4 items out of the 6 interference items using the formula: (sum of scores for the items answered) / (number of items answered). If a subject scores fewer than 4 items, the interference score will be missing.

For the severity score and interference score, descriptive statistics (n, mean, SD, median, 25th and 75th percentiles) will be provided for the actual scores and changes from baseline scores at each scheduled assessment time point.

Subjects with an evaluable baseline score and at least one evaluable post baseline score during the treatment period will be included in the change from baseline analyses. Missing data items in a scale will be handled according to the manual for each instrument. No imputation will be applied if the total or subscale scores are missing at a visit.

The additional subjects who were intolerant to the last TKI and were in MMR already at baseline will be assessed for the change in PRO from baseline by using FAS 2.

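### The last MDASI-CML window in SAP Table 2-3 closes on its target day, so read literally 7 of the 15 permitted Week 144 visit days map to no visit

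*SAP*

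**What the plan says.** SAP Section 2.1.1, Table 2-3, lists the time windows for the MDASI-CML by-visit summary.

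- The EOT (Week 144) row has target Day 1009 and interval "Day 926 to day 1009". The table's footnote fixes the origin: "Day 1 = Date of randomization".
- The general rule below the table sets the target for Week k at 7k + 1. The lower limit is the previous upper limit plus one. The upper limit is the target plus the integer part of half the distance to the next applicable visit.
- On mapping, the same section says: "Each assessment (including the end of treatment assessment), either scheduled or unscheduled, will have a mapped visit assigned", according to the defined window.
- Protocol Section 8 says: "Study visits after Week 12 (from Week 24) to EOT should be completed every 12 weeks on the designated date", with 7 days allowed either side. Week 1 Day 1 itself has a tolerance of one day either side.
- SAP Section 2.10 gives the PRO aim as covering "health related patient quality of life from baseline through end of treatment", summarised descriptively at each scheduled time point. SAP Table 1-1 lists this as a secondary objective in both cohorts.

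**The concern.** A visit window exists to catch compliant visits on both sides of the target. The EOT row reaches 83 days back and no days forward, while the protocol treats a visit up to 7 days late as on schedule. There is no later PRO row to take such a questionnaire. No other scheduled questionnaire can stand in for it either: after Week 48 the instrument is given at Weeks 72, 96, 120 and EOT (protocol Table 8-1, footnote 12), so the Week 132 visit has none. A patient who completes treatment and answers on Day 1012 would be missing at the final time point unless an unscheduled questionnaire happened to fall in the window.

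At stake is the sample size of the final row of the change-from-baseline table in FAS and FAS 2, which is the row that answers the end-of-treatment part of the PRO objective.

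**Working it through.** **1. Reproduce the table.** Apply the general rule (target = 7k + 1; upper limit = target + integer part of half the gap to the next target).

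| Visit | Target | Rule gives | Table 2-3 | Days after target |
|---|---|---|---|---|
| Week 4 | 29 | 2–57 | 2–57 | 28 |
| Week 12 | 85 | 58–127 | 58–127 | 42 |
| Week 24 | 169 | 128–253 | 128–253 | 84 |
| Week 48 | 337 | 254–421 | 254–421 | 84 |
| Week 72 | 505 | 422–589 | 422–589 | 84 |
| Week 96 | 673 | 590–757 | 590–757 | 84 |
| Week 120 | 841 | 758–925 | 758–925 | 84 |
| EOT (Week 144) | 1009 | 926–undefined | 926–1009 | 0 |

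Seven rows reproduce exactly. In the last row the target (144 × 7 + 1 = 1009) and the lower limit (925 + 1 = 926) reproduce. The upper limit does not, because the rule needs a next visit and there is none.

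**2. Look for a rescue elsewhere in the SAP.**

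- The note that EOT assessments are mapped to time points as needed stands under Table 2-1 (molecular response) only.
- Table 2-2 (cytogenetic response) assigns EOT by label. Table 2-3 does not.
- The molecular window at Week 144 runs from 144 × 7 − 40 = Day 968 to 144 × 7 + 43 = Day 1051, which is 42 days past target.
- The 144-week treatment maximum does not exclude these questionnaires. SAP Section 2.1.1 includes efficacy data up to the EOT visit, SAP Section 2.2 counts PROs among the efficacy analyses, and the final data cut-off is 30 days after the end of study treatment.

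**3. Count the permitted days that are lost.** If Week 1 Day 1 is the day of randomization, permitted days are 1009 ± 7, so Day 1002 to Day 1016, 15 days in all. Days after 1009: 7 of 15 = 47%. If the visit schedule runs d days behind randomization, the count is (7 + d)/15:

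- d = −1: 6/15 = 40%
- d = 1: 8/15 = 53%
- d = 2: 9/15 = 60%

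The only related figure in the documents is the one-day tolerance at Week 1 Day 1; d = 2 is an assumption. A negative d is unlikely, because the regimen is assigned by IRT at randomization and dosing follows it.

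**4. From days to patients (assumption).** The documents give no distribution of visit dates. For visits symmetric about the target, with a share p exactly on Day 1009, the unmapped share is (1 − p)/2:

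- p = 1/15 (evenly spread): 47%
- p = 20%: 40%
- p = 30%: 35%
- p = 50%: 25%

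**5. Effect on precision.** With a share L lost, the standard error of the mean change is multiplied by √(1/(1 − L)):

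- L = 25%: √(1/0.75) = 1.15
- L = 7/15: √(15/8) = 1.37
- L = 8/15: √(15/7) = 1.46
- L = 9/15: √(15/6) = 1.58

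For scale, FAS 2 has up to 30 patients. If all completed with visits spread evenly, 30 × 7/15 = 14 would leave the EOT row.

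**The case against.** The best defence is that the SAP nowhere says these questionnaires are dropped. It says each assessment, EOT included, will be assigned a visit. The row is labelled EOT, end of treatment is a planned PRO time point, and a sensible programmer would put a Day 1012 EOT questionnaire there. This stands in part: the text conflicts with itself and is not a clear exclusion rule. But the mapping sentence ties assignment to the defined window, and the defined window ends at Day 1009. Mapping by label would depart from the table as written.

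A reader might also infer that about half of completers' questionnaires are certain to be lost. The documents do not support that. Seven of 15 is a share of calendar days. The protocol asks for visits on the designated date, and a visit exactly on Day 1009 is kept. Larger losses can be produced by assuming a longer gap between randomization and first dose (3 days gives 10/15 = 67%), but no such gap is stated.

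Nor do the documents support a claim of bias. Exclusion would turn on a few days of scheduling, and nothing links those days to symptom scores. What can be shown is lost precision in one row.

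Finally, the endpoint is descriptive, no secondary efficacy endpoint is tested, and all assessments are still listed. That limits the weight of the point but does not remove it.

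**Conclusion.** Table 2-3 is wrong as written in one cell. That the window closes on its target, that the protocol allows visits 7 days later, and that no other rule supplies a PRO window for Day 1010 onward all follow directly from the text. The size of the loss does not. It is 7 of 15 permitted days, or 8 of 15 with a one-day lag. As a share of questionnaires it is roughly 25% to 47% if visits are symmetric about the target and there is no lag, and up to about 60% if visits are evenly spread and dosing starts 1 to 2 days after randomization. The standard error at EOT would be about 1.15 to 1.6 times what it need be.

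The consequence is confined to the EOT row of the MDASI-CML summary in FAS and FAS 2. The Week 4 to Week 120 rows and the primary analysis are untouched. The point is modest in weight and worth correcting because the correction is so simple.

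**What to change.** In Table 2-3, change the EOT (Week 144) interval to Day 926 up to and including the EOT visit. Keep the existing rule that the questionnaire closest to Day 1009 is used. In the general rule below the table, add that the last scheduled visit has no upper limit other than the EOT visit.

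This is safer than a fixed limit of Day 1016, which would miss Day 1017, a permitted day when first dose is one day after randomization. A limit of 1009 + 84 = Day 1093 would also cover every permitted day, but it is not needed: the SAP already keeps data after the EOT visit out of these summaries, so an open end admits nothing unwanted.

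The cost is one table cell and one sentence, recorded in a SAP addendum before the end-of-study-treatment database is locked. No new data are needed.

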2.2 Analysis sets

The subject population for the study includes subjects resistant or intolerant to 2 or more prior TKI treatments without MMR at baseline, and an additional group of subjects who were intolerant to the last TKI and were in MMR at baseline. Note that the YR data domain from IRT will be used to identify the stratification groups for the study population, and the biomarker data (B1 domain) containing BCR::ABL ratio will be used to confirm the MMR status at baseline for all subjects. If there is discrepancy between YR and B1 data, the MMR status at baseline will be assessed based on the B1 data.

The Analysis Sets are stated as follows:

Full Analysis Set

The Full Analysis Set (FAS) comprises all participants to whom study treatment has been assigned by randomization except the additional subjects who were intolerant to the last TKI and were in MMR at baseline.

Full Analysis Set 2

The Full Analysis Set 2 (FAS 2) comprises only the additional subjects who were intolerant to the last TKI and were in MMR at baseline and to whom study treatment has been assigned by randomization.

Safety Set

The Safety Set (SAF) includes all participants who received at least one dose of study treatment except the additional subjects who were intolerant to the last TKI and were in MMR at baseline.

Safety Set 2

The Safety Set 2 (SAF 2) includes only the additional subjects who were intolerant to the last TKI and achieved were in MMR at baseline and who received at least one dose of study treatment.

Unless otherwise stated, the analysis sets will be applied as below:

- For the subjects resistant or intolerant to 2 or more prior TKI treatments without MMR at inclusion to the trial
 - The FAS will be used for demographics and baseline characteristics (except disease characteristics) and all efficacy analyses including PROs
 - The SAF will be used for baseline disease characteristics, exposure and all safety analyses
- For the additional subjects who were intolerant to the last TKI and were in MMR at baseline
 - The FAS 2 will be used for demographics and baseline characteristics (except disease characteristics) and selected efficacy analyses including PROs
 - The SAF 2 will be used for baseline disease characteristics, exposure and selected safety analyses

Withdrawal of Informed Consent

Any data collected in the clinical database after a subject withdraws informed consent from further participation in the trial will not be included in the analysis. The date on which a subject withdraws consent is recorded in the eCRF.

Novartis will continue to retain and use all research results (data) that have already been collected for the study evaluation, including processing of biological samples that has already

started at time of consent withdrawal/opposition. No new Personal Data (including biological samples) will be collected following withdrawal of consent/opposition.

2.2.1 Subgroup of interest

Subgroup analyses of the primary efficacy endpoint to assess the homogeneity of the treatment effect across demographic and baseline disease characteristics may be conducted on the following subgroups, if there are at least 10 subjects in each category:

- Gender: Male and Female
- Race: Asian, Caucasian, or others
- Age at baseline (≥ 18 -< 65 years, ≥ 65 years, ≥ 75 years)
- Reason for discontinuation of the last prior TKI: Warning or failure (i.e. lack of efficacy) or intolerance (i.e. adverse event, lack of tolerability) to the most recent TKI therapy at the time of screening

Note: Only one reason for discontinuation is allowed for each prior therapy.

- Number of prior TKI therapies: 2, 3 or ≥ 4
- Cytogenetic response status at baseline: Major (MCyR) - 0 to 35% Ph+ metaphases; Complete (CCyR) - 0% Ph+ metaphases; Partial (PCyR) - >0 to 35% Ph+ metaphases; Minor (mCyR) - >35 to 65% Ph+ metaphases; Minimal - >65 to 95% Ph+ metaphases; or None - >95 to 100% Ph+ metaphases.
- Prior TKI treatment: imatinib, nilotinib, dasatinib, bosutinib, radotinib or ponatinib
- Prior ponatinib: Yes or No
- Mutation status at baseline: Non-mutant or mutant

Other subgroup may be analyzed as appropriate.

2.3 Subject disposition, demographics and other baseline characteristics

2.3.1 Subject disposition

The number (%) of randomized subjects included in the FAS and FAS2 will be presented overall and by treatment group (40mg bid or 80mg qd). The number (%) of screened and not-randomized subjects and the reasons for screening failure will also be displayed. The number (%) of subjects in the corresponding analysis set who are still on treatment, who discontinued the study phases and the reason for discontinuation will be presented overall and by treatment group (40 mg bid or 80 mg qd).

The following summaries will be provided (with % based on the total number of subjects):

- Number (%) of subjects who were randomized (based on data from IRT system)
- Number (%) of subjects who were randomized but not treated (based on study treatment eCRF page not completed for any study treatment component)

- Primary reason for not being treated (based on “Disposition” eCRF page)
- Number (%) of subjects who were treated (based on study treatment eCRF pages of each study treatment completed with non-zero dose administered)
- Number (%) of subjects who are still on-treatment (based on the “subject status” and “Treatment Disposition” page not completed);
- Number (%) of subjects who discontinued the study treatment phase overall, before Week 48 and Week 96 (based on the “Subject status” and “Disposition” page)
- Primary reason for study treatment phase discontinuation overall, before Week 48 and Week 96 (based on the “Disposition” page).

Separate disposition tables will be presented for subjects with dose escalation.

Protocol deviations

The number (%) of subjects in the FAS and FAS2 with any protocol deviation will be tabulated by deviation category (as specified in the Study Specification Document) overall. All protocol deviations will be listed. In addition, the number (%) of subjects in the FAS and FAS2 with any COVID-19 related protocol deviation (COVID-19 specific protocol deviations as well as non-specific COVID-19 protocol deviations with a COVID-19 relationship) during the treatment period will be tabulated by deviation category (as specified in the Study Specification Document) overall.

Analysis sets

The number (%) of subjects in each analysis set (defined in [Section 2.2](#)) will be summarized.

